9.8 Analysis of Safety Endpoints

9.8.1 Study Drug Exposure and Compliance

Subject exposure to treatment will be summarized by treatment period and overall. The duration of exposure, number of doses administered per subject, total volume (μ L) administered, and total dose (μ g) will be summarized using descriptive statistics (n, mean, SD, median, minimum, and maximum). In addition, the prior oral levothyroxine dose (μ g) will be summarized using descriptive statistics (n, mean, SD, median, minimum, and maximum).

Subject dose level by visit will be summarized by subject counts and percentages.

9.8.2 Adverse Events

The number and percentage of subjects with AEs as well as event counts will be summarized by MedDRA-coded SOCs and PTs. The following AE summaries will be presented by treatment period and overall:

- Overall summary of events including
 - Any AEs
 - Any TEAEs
 - Any drug-related TEAEs
 - Any severe TEAEs
 - Any serious TEAEs
 - Any drug-related serious TEAEs
 - Any TEAEs leading to death
 - Any TEAEs leading to premature discontinuation of study drug
 - Any serious TEAEs leading to premature discontinuation of study drug
- Summary of all TEAEs by SOC and PT
- Summary of all TEAEs by SOC, PT, and severity
- Summary of all TEAEs by SOC, PT, and relationship
- Summary of serious TEAEs by SOC and PT
- Summary of TEAEs leading to premature discontinuation of study drug by SOC and PT
- Summary of all TEAEs by descending PT overall
- Summary of TEAEs occurring in 10% of subjects overall

Within each summary, a subject will be counted only once within each SOC and PT for the number and percentage of subjects, but will be counted for each occurrence of the AE for the event counts. TEAEs summarized by severity will count each subject once by maximum severity within each SOC and PT. TEAEs summarized by relationship will count each subject once in the order of Related, Not Related within each SOC and PT.

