## 13.7. Safety and Tolerability

All safety analyses will be performed using the Safety population. Safety data will be collected and summarized by study period (Titration Period, Maintenance Period). No formal hypotheses will be tested on safety data.

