### 13.7.1. Adverse Events

Adverse events will be coded using the Medical Dictionary for Regulatory Activities (MedDRA) version 25.0 or higher. Listings of all AEs, treatment-emergent SAEs, and TEAEs leading to study discontinuation will be provided by subject, study period, verbatim term, MedDRA System Organ Classification (SOC) and Preferred Term (PT), start and end dates, seriousness, severity, relationship to study drug, action taken with study treatment, and outcome.

AEs will be summarized overall by the number and percentage of subjects who experienced at least one AE of the following categories in each study period: any AE, any TEAE, any drug-related TEAE, any severe TEAE, any serious TEAEs, any drug-related SAE, any SAE leading to death, any TEAE leading to premature discontinuation of study drug, and any SAE leading to premature study drug discontinuation.

The number and percentage of subjects reporting a TEAE in each study period and overall (while taking XP-8121) will be tabulated by SOC and PT; by SOC, PT, and severity (mild, moderate, and severe); and by SOC, PT, and relationship to study drug.

The number and percentage of subjects reporting an SAE or reporting a TEAE leading to premature discontinuation of study drug in each study period and overall will be summarized by SOC and PT.

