3.2 Secondary Objectives

Secondary objectives of this study are:

- To determine a dose range of XP-8121 capable of maintaining normalized TSH following a switch from stable replacement therapy with oral levothyroxine
- To evaluate a safe initiation dose of XP-8121 based on the prior stable dose of oral levothyroxine
- To evaluate a safe titration scheme for dosing XP-8121 to TSH target

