4. STUDY DESIGN

4.1 General Design

Only a synopsis of the study is presented herein, full details can be found in the protocol. This is a non-randomized, open-label, single arm, self-controlled study of XP-8121 to determine a target dose conversion factor from stably dosed oral levothyroxine to XP-8121 in subjects with hypothyroidism and to assess the safety and tolerability of XP-8121 after once-weekly SC injections.

This study includes the following periods: Screening, Titration Period, and Maintenance Period. The study will conclude with an End of Maintenance or Early Termination (ET) Visit. The XP-8121 initiation dose will correspond to 50% of the target weekly dose of XP-8121 SC (in μ g), which is calculated as the current daily oral levothyroxine dose multiplied by 4, rounded up to the nearest 50 μ g.

During the Titration Period, subjects will come into the clinic once a week for at least 2 and up to 8 weeks, as applicable, for dosing administration. Based on free thyroxine (fT4) levels, XP-8121 will be titrated biweekly (every other week) by intervals of 25% of the target dose. TSH and T4 (free and total) will be checked weekly. A safety check will be completed 72 hr. (\pm 1 day) after the initial dose and each escalation during the Titration Period. If fT4 exceeds the upper limit of normal during titration, the XP-8121 dosage will be lowered and held at the previously tolerated dose.

[figure not shown]
Once subjects have completed the Titration Period, they will continue at the same dose of XP-8121 in the Maintenance Period for 4 weeks, returning to the Clinical Research Unit (CRU) on a weekly basis for dosing. An End of Maintenance Visit will be performed at Day 29 (1 week after the last XP-8121 dose). Subjects not achieving an adequate fT4 at \leq 125% of the target dose or the maximum weekly dose of 1500 μ g may also continue into the Maintenance Period at the discretion of the Investigator and after conferring with the Medical Monitor. Titration details are outlined in Appendix A of the study protocol.

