6.9.2 Adverse Events

AE verbatim terms recorded by the investigator will be coded to system organ class (SOC) and preferred term (PT) using the Medical Dictionary for Regulatory Activities (MedDRA) version 26.0.

A TEAE is defined as any adverse event which occurs on or after the first dose of study drug.

All TEAEs will be assessed by the investigator for severity and for causality. Events with missing severity will be summarized as Severe. Events with missing relationship to study treatment will be summarized as related.

TEAEs marked with a relationship to study treatment of definitely related, probably related, possibly related, or missing will be considered as related TEAEs, and TEAEs summarized by relationship will count each subject once for the maximum relationship within each SOC and PT.

TEAEs will be attributed to treatment periods by comparing the start date/time of the event to the date/time of first dose within each of the treatment periods.

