7. ANALYSIS SETS

Analysis Set	Definition	Used for Analyses
Safety Population	All subjects who received at least one dose of XP-8121.	Disposition, Demographics, Medical History, Disease History, Concomitant Medications, Deviations, Safety Analyses, Tolerability endpoints Secondary endpoints, Exploratory endpoints (except PK related endpoints)
Completer Population	All subjects who completed the Maintenance Period and exhibit normalized TSH throughout the Maintenance Period while on a stable dose for approximately 6 weeks. Subjects with a reduced dose at any point during the Maintenance Period will not be included.	Dose Conversion Factor analysis, Sensitivity analysis of Change from Baseline of Blood Thyroid Hormone Concentrations Secondary Endpoint
PK Population	All safety population subjects who participated in the PK sub-study, who do not have any major protocol deviations affecting the PK endpoints and for whom a sufficient number of samples is available to determine at least one PK parameter.	PK analyses

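### The planned adverse event tables are split only by study period, so they give no incidence by dose level, although a safe initiation dose and a safe titration scheme are stated objectives

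*SAP*

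**What the plan says.** **Objectives.** SAP 3.2 (and protocol 6.1.2) lists as secondary objectives the evaluation of a safe initiation dose and "To evaluate a safe titration scheme for dosing XP-8121 to TSH target". Protocol 5.5 names safe starting doses and feasible titration schedules among the study's goals and says the findings will inform a later trial.

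**Dosing.** SAP 4.1 sets the start: "The XP-8121 initiation dose will correspond to 50% of the target weekly dose of XP-8121 SC". It then says: "XP-8121 will be titrated biweekly (every other week) by intervals of 25% of the target dose". Protocol 7.4.2 caps the dose at 125% of target or 1500 µg, whichever is lower. Titration lasts 2 to 8 weeks, and subjects enter Maintenance at the level they have reached. Protocol 7.4.3 allows a reduction of one level during Maintenance.

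**AE tables.** SAP 9.8.2: "The following AE summaries will be presented by treatment period and overall". Protocol 13.7.1 uses the same split: "The number and percentage of subjects reporting a TEAE in each study period and overall". SAP 6.9.2 assigns events to a period, not to a dose: "TEAEs will be attributed to treatment periods by comparing the start date/time of the event to the date/time of first dose" within each period.

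**Population.** Protocol 13.7: "All safety analyses will be performed using the Safety population". SAP 7 defines that set as follows: "All subjects who received at least one dose of XP-8121". SAP 9.8.2 gives no denominator for a period's percentages. SAP 9.6, for normalized TSH, gives two: the Safety Population and the subjects entering Maintenance.

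**The concern.** Two secondary objectives ask about safety at particular points of the dosing scheme: the first dose level and the steps after it. The AE tables are split by a different variable. The Titration column adds together events at up to four dose levels. The Maintenance column adds together subjects settled at different levels, some of them reduced during the period. Neither document plans an AE table by dose level, by time since an up-titration, or per unit of exposure.

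A team designing the next trial would want to know whether events cluster at the start, at the upper steps, or evenly. The planned AE tables would look the same in all three cases.

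A related gap concerns laboratory values. Low/Normal/High counts are given visit by visit (SAP 6.7 and 9.6). No table counts how many subjects were ever above the free T4 upper limit or below the TSH lower limit, or at which dose level. Over-replacement is one of the two risks that protocol 7.4.2 says the titration rate is meant to limit.

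**Working it through.** The documents give no figure for the AE tables, so there is no stated value to reproduce. The sample-size calculation does not bear on this point. The only figure taken from it is the 44 subjects to be enrolled.

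**1. Number of dose levels in the Titration column.** Start 50%, step 25%, maximum 125% of target: (125 − 50)/25 + 1 = 4 levels. At two weeks per level that is 4 × 2 = 8 weeks, which matches the stated maximum length of Titration. Protocol 7.4.2 raises the dose when free T4 is below or within range without signs of excess, so passing through several levels is the expected course. Subjects held at the 1500 µg cap may not reach 125%.

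**2. What pooling hides.** Assumptions: every subject passes through all four levels, risks at each level are independent, and the risks are illustrative, not from the documents. Titration incidence = 1 − Π(1 − pᵢ).

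| Assumed risk at 50 / 75 / 100 / 125% | Calculation | Titration incidence |
|---|---|---|
| 20 / 5 / 5 / 5% | 1 − 0.80 × 0.95³ | 31.4% |
| 5 / 5 / 5 / 20% | 1 − 0.95³ × 0.80 | 31.4% |
| 9 / 9 / 9 / 9% | 1 − 0.91⁴ | 31.4% |

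A problem at the initiation dose, a problem at the top dose and a flat risk all produce the same Titration entry.

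**3. What other planned outputs add.**
- Dose level by visit (SAP 9.8.1) is not crossed with AEs.
- ECG, vital signs and thyroid hormones are summarized by visit and local tolerability by collection timepoint. The first two Titration weeks and the first 72-hour visit are at 50% of target for everyone, so these outputs do describe the initiation dose. At later visits subjects are at different levels, so visit no longer stands for dose.
- The boxplot in SAP 9.6 shows free T4 after the first dose, by starting dose.
- AE listings carry start dates but, in the fields named in protocol 13.7.1, not the dose at onset.

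None of these is AE incidence by dose level.

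**4. Denominator for Maintenance.** Let M be the number of subjects dosed in Maintenance. M is not given, so it is varied here. If the full Safety Population of 44 were the denominator, the displayed percentage would be M/44 of the percentage among those dosed.

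| M (assumed) | M/44 | 10 subjects with events: 10/M | 10/44 |
|---|---|---|---|
| 44 | 1.000 | 22.7% | 22.7% |
| 42 | 0.955 | 23.8% | 22.7% |
| 40 | 0.909 | 25.0% | 22.7% |
| 38 | 0.864 | 26.3% | 22.7% |
| 34 | 0.773 | 29.4% | 22.7% |

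The effect ranges from none to a modest lowering. For scale, the exact 95% confidence interval for 10/44 is 11% to 38%.

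**The case against.** **The safety output as a whole is not blind to dose.** This stands. The by-visit summaries for the first two weeks and the 72-hour visit cover the initiation dose in all subjects. A 72-hour visit also follows each up-titration. Every dose is given and recorded at the research unit, AE start dates are listed, and spaghetti plots show each subject's free T4 and TSH. With about 44 subjects, dose at onset could be worked out by hand. A reader might infer that the plan cannot assess the initiation dose at all, or that the free T4 boxplot is the only display bearing on it. The documents do not support either. The gap is in the AE tables.

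**Dilution of Maintenance rates is not written in the plan.** This also stands. A reader might infer from the Safety Population rule that Maintenance percentages divide by everyone ever dosed. The SAP names the analysis set but not the column denominator, and the table shells are in a separate document. An M of 38 may also be too low: the allowance from 38 to 44 covers TSH non-normalizers as well as non-completers, and non-normalizers at study end have entered Maintenance.

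**Step-down does not follow every excursion.** Lowering is prescribed for free T4 above the upper limit during Titration (protocol 7.4.2). In Maintenance the Investigator may reduce (7.4.3), and Titration has no corresponding rule for low TSH. The case for an ever-out-of-range count is that visit-by-visit counts cannot be added up to a number of subjects. It does not depend on step-down.

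**Tables by dose would be weak evidence.** Partly right. About 4 of 44 against 9 of 44, roughly the 9% and 20% risks above, gives a Fisher p-value of 0.23. Dose level is also confounded with time on treatment and with who tolerates escalation. That limits how the tables may be read, but it is no reason to leave them out of a descriptive safety analysis.

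**Conclusion.** The point holds for the AE tables. They are by period and overall only, they pool 50 to 125% of target, and no planned table gives AE incidence by dose, although two secondary objectives concern the initiation dose and the titration steps. Other outputs give partial information.

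The size of the loss cannot be computed from the documents. The 31.4% example shows only that opposite dose patterns can give the same Titration entry, under assumed risks, independence and full passage through four levels.

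On the denominator, the supportable statement is that it is unstated. If the full Safety Population were used, Maintenance percentages would be lowered by the factor M/44: nothing if all 44 enter, and a relative 13.6% (1 − 38/44) if 38 do.

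This is a cheap improvement worth making. It does not undermine the primary analysis of the conversion factor.

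**What to change.** 1. **SAP 9.8.2:** add descriptive TEAE tables by dose level at onset, as percent of target (50, 75, 100, 125%), taking the most recent dose administered before onset. Show the number of subjects exposed and the person-weeks at each level. State how levels limited by the 1500 µg cap are classed.
2. **SAP 9.6:** add the number of subjects ever above the free T4 upper limit, and ever below the TSH lower limit, by dose level at the time of the result.
3. **SAP 9.8.2:** state that percentages for a period use the subjects dosed in that period.
4. **Interpretation:** say in the text that these tables are descriptive, that dose level is confounded with time and with tolerance of escalation, and that they do not establish which step causes events.

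**Cost:** a few more tables and two or three sentences. The dosing records, AE onset dates and times, and scheduled TSH and T4 results are already collected, so no visit, sample or dosing rule changes. The drawback is small counts per level. Fixing the groupings in advance avoids choosing them after the events are known.

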9.8.3 Clinical Laboratory Assessments

Visit values and changes from baseline to each post-baseline visit will be summarized with descriptive statistics (n, mean, SD, median, minimum, and maximum) for all chemistry, hematology, and urinalysis measures. Box plots of observed results and changes from baseline for chemistry, hematology, and urinalysis at each timepoint will be presented. A data table will be displayed under the plot with the mean value and the number of subjects with data at each timepoint.

All laboratory results will be displayed in a listing, and results that are outside the normal range will be identified on the listing as either high or low and CS. Separate listings for abnormal and CS laboratory results will be provided. Historical laboratory assessments will be listed.

9.8.4 Electrocardiograms

Visit values and changes from baseline to each post-baseline visit will be summarized with descriptive statistics (n, mean, SD, median, minimum, and maximum) by treatment period for all ECG parameters:

heart rate (beats/min), QT interval (ms), PR interval (ms), QRS interval (ms), RR interval (ms), QTcF (ms) and QTcB (ms).

Subject counts and percentages for ECG interpretation and clinical significance as reported on the eCRF by the investigator (and confirmed by cardiologist) will be presented for visit results and shifts from baseline to each visit. Cardiologist's overread will take precedence if it differs from investigator's assessment.

9.8.5 Vital Signs

Visit values and changes from baseline to each post-baseline visit will be summarized with descriptive statistics (n, mean, SD, median, minimum, and maximum) by treatment period for all vital signs: SBP (mmHg), DBP (mmHg), pulse rate (beats/min), respiration rate (breaths/min), temperature (C), and weight (kg).

CS categories for relevant vital signs will be summarized with subject counts and percentages by treatment period. CS results will be summarized by unique subject counts for any CS result, any CS Low result, and any CS High result within each measure and across all measures.

9.8.6 Physical Examination

Physical examination results will be listed.

9.8.7 Local Tolerability

The Modified Draize Scale, Injection Site Discomfort, time until onset (minutes), and duration of discomfort (minutes) will be summarized by descriptive statistics (n, mean, SD, median, minimum, and maximum) by each collection timepoint.

Discomfort description (i.e., pain, irritation, itching, etc.), each severity category for erythema/edema on the Modified Draize Scale, and the category of Injection Site Discomfort Intensity will be summarized by count and percentage by each collection timepoint.

9.9 Subgroup Analyses

If a sufficient number of subjects with secondary or tertiary hypothyroidism are included in the study, additional analyses for the secondary efficacy endpoints and non-PK exploratory endpoints may be performed on all subjects regardless of hypothyroidism diagnosis at the discretion of the sponsor.

10. COMPUTER SOFTWARE

Statistical analyses will be performed using SAS® version 9.4 or higher in a Windows environment, or R version 4.1.1 or higher, or Phoenix WinNonlin™ version 8.3 or higher.

12. APPENDIX

Not applicable.

13. TABLE/FIGURE/LISTING SHELLS

The mock shells for the tables/figures/listings will be provided in a separate document.
